Statistical Analysis Plan (Addendum)

**A structured telephone-delivered intervention to reduce methamphetamine use
(Ready2Change-Methamphetamine, R2C-M)**

ClinicalTrials.gov Identifier: [NCT04713124](https://clinicaltrials.gov/ct2/show/NCT04713124)

Pre-registered: 19 January 2021

Version: 1

Date version finalised: 1 August 2025

Background

Australia has one of the highest rates of methamphetamine (MA) use in the world; however, uptake of in-person psychological treatment remains extremely low due to numerous individual (e.g. stigma, shame) and structural (e.g. service accessibility, geographical location) barriers to accessing care. Telephone-delivered interventions are ideally placed to overcome many of the known barriers to treatment access and delivery. This randomised controlled trial (RCT) will examine the efficacy of a standalone, structured telephone-delivered intervention to reduce MA problem severity and related harms.

Study rationale and design

This study is a double-blind, parallel-group RCT. We planned to recruit between 188 and 204 individuals with mild to moderate MA use disorder from across Australia. Provision was made to increase the recruitment target, based on the 3 and 6 month attrition rates observed after recruitment and data collection commenced (after 12 months of data collection with this complex cohort, 3 and 6 month attrition rates were higher than anticipated). As such, the target sample size was increased from 188 subjects, to up to 204 participants (i.e. an additional 8 subjects based on the 3 month attrition rate; or an additional 16 subjects based on the 6 month attrition rate). After eligibility and baseline assessments, participants were randomly allocated to receive either the Ready2Change-Methamphetamine (R2C-M) intervention (four to six telephone-delivered intervention sessions, R2C-M workbooks and MA information booklet) or control (four to six ≤5-min telephone check-ins and MA information booklet including information on accessing further support).

Telephone follow-up assessments occurred at 6 weeks and 3, 6 and 12 months post-randomisation. The primary outcome was change in MA problem severity (Drug Use Disorders Identification Test, DUDIT) at 3 months post-randomisation. Secondary outcomes (measured at some or all timepoints of 6 weeks and 3, 6 and 12 months post-randomisation) included MA problem severity (DUDIT) at 6 and 12 months post-randomisation, amount of methamphetamine used, number of DSM-5 methamphetamine use disorder criteria met, cravings, psychological functioning, psychotic-like experiences, quality of life and days of other drug use. Mixed-methods program evaluation were planned to be performed and cost-effectiveness was planned to be examined.

Statistical Analysis Plan (SAP)

This plan, or SAP Addendum, provides additional detail on the project and statistical considerations previously documented on ClinicalTrials.gov ([NCT04713124](https://clinicaltrials.gov/ct2/show/NCT04713124)) and published <https://pubmed.ncbi.nlm.nih.gov/36991490/>. Additional analyses not specified in the published protocol or this addendum will be regarded as exploratory.

Statistical software

Analysis will be conducted using the most appropriate procedures in programs such as GenStat, R, SAS, SPSS and/or Stata.

Analytic approach

Data will be collated, cleaned and validated using programmed edit checks, in a database that will be locked prior to the unblinding of the statistician for the primary analysis. The primary analysis will take place after all subjects, not known to have withdrawn or not deemed lost to follow-up, have had their 12-month assessments and will be based on the intention-to-treat principle (i.e. subjects' data are analysed as randomised and as stratified). A “per-protocol” sensitivity analysis will be restricted to those subjects with at least one follow-up assessment and, for subjects randomised to the R2C-M arm, participation in at least two telephone counselling sessions. Previous research delivering the R2C program to people with alcohol use disorder found exposure of ≥ 2 sessions yielded a reduction in alcohol use severity compared to a control arm (Lubman et al. 2022).

The first R2C session focuses on a clinical assessment and identifying treatment goals and the second session is when a therapeutic dose is received. As such, exposure to ≥ 2 sessions is considered “as-treated” for the per-protocol analysis. Additional sensitivity analyses will include a covariate for the number of structured telephone counselling sessions [1 to 6] in which subjects, in the R2C arm, participated. The repeated measurements of the outcome variables will be analysed by fitting linear mixed models using restricted maximum likelihood (REML)—this will allow the most suitable variance-covariance model for the repeated measures to be selected, using Akaike’s Information Criterion, and commonality of nonlinear trends over time to be explored via splines. The F-test will be used to test for an overall group by time interaction and the primary comparison, between groups, of their changes from baseline to 3-month follow-up will be based on a t-test of the corresponding interaction contrast—this t-test will utilise the predicted means and their variance-covariance matrix which are recovered from the fitted mixed model.

Diagnostic plots of residuals will be assessed and, if deemed necessary, variance-stabilising transformations such as the empirical logistic transformation will be applied to the outcome variables, and inferences will be based on the analyses conducted on the transformed scale. In a series of exploratory analyses, mixed models with covariates for gender, illicit drug use, extent of exposure to the intervention, differences due to assigned counsellor, exposure to other treatments/programs and baseline levels of MA use, psychological distress, depression, anxiety and stress will be fitted, including their interactions with treatment group, in order to identify moderating factors. As these analyses will be exploratory, we will not adjust alphas in these analyses. As parsimony will be the aim of the exploratory analyses, the most restricted model will be selected. The complete list of candidate covariates and details of the analyses will be specified in a Statistical Analysis Plan that will be reviewed and approved by a Study Management Committee prior to database lock. No interim analyses will be conducted and there are no plans

to halt data collection before completion. Analyses will be conducted using the most appropriate procedures in GenStat, R and Stata.

1. Statistical analysis of the primary outcome: Drug Use Disorders Identification Test (DUDIT) (Primary outcome and key secondary outcome)

The primary outcome variable is change in methamphetamine problem severity at 3 months, assessed by the DUDIT. Scores range 0–44. Higher score suggests more severe MA use problem. The DUDIT will also be used as a secondary outcome measure (assessed at 6 and 12 months post-randomisation). The time frame has been adapted to cover the month prior to assessment (rather than the year) and thereby enable follow-up assessments at 3 months (primary outcome), 6 and 12 months (secondary outcomes). **Items of the DUDIT were adapted to focus on methamphetamine specifically, rather than any drug use.**

The following guidance will be used for calculating the DUDIT scores:

Muller, A. E., Havnes, I. A., Rognli, E. B., & Bukten, A. (2018). Inmates with Harmful Substance Use Increase Both Exercise and Nicotine Use Under Incarceration. International journal of environmental research and public health, 15(12), 2663. <https://doi.org/10.3390/ijerph15122663>

For the primary outcome (DUDIT), missing values in the items that comprise the total DUDIT score will be accommodated as follows: "Harmful drug use was indicated by ≥ 6 for men and ≥ 2 for women on the DUDIT. Both the AUDIT and DUDIT were scored for those who answered at least five items in each, and these individuals' missing items were replaced by the individual means, following the recommendations of Hawthorne and Elliot" (Muller et al. 2018)

Inferences about the effect of R2C on the primary outcome will be based on the comparison, between treatment groups, of their changes from baseline to 3 months follow-up. This comparison will be based on a t-test of the corresponding interaction contrast – this t-test will utilise the predicted means and their variance-covariance matrix that are recovered from the fitted mixed model for all repeated assessments up to and including 12 months.

The following sequence of mixed model analyses will be conducted:

- (1) Analyse the raw (i.e. untransformed values) with an independence (i.e. equicorrelation) model for the repeated measurements
- (2) Check residual variance assumptions using diagnostic residual plots and, if deemed necessary, explore the empirical logit transformation. Determine the measurement scale (raw or transformed).

- (3) For the selected measurement scale, investigate three alternative error variance/covariance models (VCVMs) - Independence, First Order Autoregressive, i.e. AR(1) and Unstructured. Models will be compared using the Akaike Information Criterion (AIC) and the VCVM model with the smallest AIC will be selected unless a more parsimonious model has an AIC within 10 units of the minimum AIC in which case the more parsimonious VCVM model will be given preference.
- (4) Declare the “definitive scale” (raw or transformed) and VCVM for the DUDIT Total Score and, if not contraindicated, use these also for the domain scores (defined as, for example: drug use frequency, problems associated with drug use).
- (5) Report the definitive analyses.
- (6) Conduct the PPS sensitivity analysis using the definitive approach identified in Step 5 and restrict this to the DUDIT Total Score.
- (7) Explore adjustments for gender, illicit drug use, extent of exposure to the intervention, exposure to other treatments or programs, level of psychological distress and, if appropriate, level of methamphetamine use at baseline (and interactions with treatment group). A full list of covariates is outlined below. As these analyses will be exploratory, we will not adjust alphas in these analyses. As parsimony will be the aim of the exploratory analyses, the most restricted model will be selected.
- (8) Explore alternative representations of the DUDIT Total Score, in particular:

Ordered symptom categories defined as:

0–1 (Women) / 0–5 (Men): No indication of problematic drug use.

2–24 (Women) / 6–24 (Men): Likely problematic drug use.

25 or more (Both genders): Suggests severe drug dependence.

Domain categories defined as, for example:

Items 1 – 3: drug use frequency

Items 4 – 11: problems associated with drug use

Matuszka B, et al. Psychometric characteristics of the drug use disorders identification test (DUDIT) and the drug use disorders identification test-extended (DUDIT-E) among young drug users in Hungary. International journal of behavioral medicine. 2014 Jun;21:547-55.

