Cost effectiveness analysis results will be presented as the mean net benefits of treatment across a range of hypothetical money values of QALYs, with 95% CIs and a one-sided p-value calculated using non-parametric bootstrapping. Net benefit estimates will be based on the between group difference in the means cost and outcome over the 12-months estimated using separate regression analyses controlling for baseline values and the stratification variable. A generalized linear regression model, with an appropriate choice of distribution, will be used to account for any skewness in the cost data. Multiple imputation will be used to address the uncertainty of the estimates due to missing observations. A secondary analysis will estimate a “per-protocol” cost-effectiveness of the intervention adjusted for non-adherence. Instrumental variable estimation will be used with the randomization group as the instrument for adherence, defined as at least two telephone counselling sessions.

Key cost-effectiveness outcomes

10. Quality-adjusted life years (QALYs) assessed with the EuroQol, 5 dimensions, 5 levels (EQ-5D-5L+)

A modified version of the EQ-5D-5L+ will be used to measure health-related quality of life for the economic evaluation. The EQ-5D-5L is a validated health measure which describes 5 dimensions of health (Mobility, Self-Care, Usual Activities, Pain/Discomfort, and Anxiety/Depression), each with 5 levels of functioning (i.e. “no problems” to “extreme problems”) (67). Four items from the Assessment of Quality of Life 8D (AqoL-8D; a widely used, validated measure of QoL) (68) related to Vitality, Sleep, Close Relationships and Community Connectedness are added to the EQ-5D-5L to create the EQ-5D-5L+ (~4 mins to administer). This composite measure has been found to capture 90% of the variation in the AqoL-8D and can be used to give an accurate prediction of that utility score, while being a shorter measure (i.e. 9 items) to reduce participant burden. For the analyses, just the EQ-5D-5L component will be utilised to calculate QALYs due to the established value sets for this aspect of the instrument. Conversion will be done using the most up-to-date utility weights:

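### The per-protocol DUDIT comparison sets an attendance condition in the R2C-M arm only, so selection can bias it in either direction; a supplementary complier estimate would keep the randomised comparison

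*SAP*

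**What the plan says.** Under 'Analytic approach', the SAP makes the primary analysis intention-to-treat and adds a per-protocol sensitivity analysis. That set is limited to subjects with at least one follow-up assessment and, "for subjects randomised to the R2C-M arm, participation in at least two telephone counselling sessions".

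The threshold is justified in two ways. An earlier trial of the programme in alcohol use disorder found a benefit at two or more sessions. And: "The first R2C session focuses on a clinical assessment and identifying treatment goals and the second session is when a therapeutic dose is received".

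Step (6) under 'Statistical analysis of the primary outcome' gives the method: "Conduct the PPS sensitivity analysis using the definitive approach identified in Step 5 and restrict this to the DUDIT Total Score". It names no adjustment for selection into attendance.

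Under 'Study rationale and design', the R2C-M arm receives "four to six telephone-delivered intervention sessions, R2C-M workbooks and MA information booklet", and the comparator is "control (four to six ≤5-min telephone check-ins" plus an information booklet. Controls therefore also have calls that can be attended or missed, but the per-protocol set places no condition on them.

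Under 'Cost-effectiveness analysis', a secondary per-protocol analysis estimates the "cost-effectiveness of the intervention adjusted for non-adherence". Its method is different: "Instrumental variable estimation will be used with the randomization group as the instrument for adherence, defined as at least two telephone counselling sessions".

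**The concern.** People who return for a second counselling session may differ from those who do not in how their methamphetamine problems would have changed anyway. Dropping the non-attenders from one arm, and keeping their counterparts in the other, mixes that difference into the treatment contrast. Analysing change from baseline removes stable differences in level, but not differences in trajectory. The dose rationale explains why the threshold is two sessions. It does not make attenders comparable with all controls.

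A per-protocol result is usually read as the effect of an adequate dose. Here it could lie above or below the intention-to-treat result through selection alone, so neither agreement nor disagreement between the two would support that reading.

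**Working it through.** The SAP states no figure for this analysis, so there is nothing to reproduce. The size has to be worked out from assumed inputs.

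**Inputs**
- From the SAP: a target of 188 to 204 participants, and the two-session threshold in R2C-M only.
- Assumed: equal allocation, and 70 to 80 per arm with data (80 of 94 is 15% lost; 70 of 102 is 31% lost).
- Assumed: share of R2C-M below two sessions, p = 0.1, 0.2 or 0.3.
- Assumed: gap d in untreated change between would-be attenders and non-attenders, from -0.5 to +0.5. Units are SDs of change, and positive means attenders improve more.

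**Bias of the restricted comparison**

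Let untreated change average mA in attenders and mN in non-attenders. Controls contain both types and average (1-p)mA + p·mN. The R2C-M per-protocol group averages mA plus the effect in attenders. The contrast is therefore

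effect in attenders + p(mA - mN) = effect in attenders + p·d.

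- p = 0.1, d = 0.25: 0.025 SD
- p = 0.2, d = 0.5: 0.10 SD
- p = 0.3, d = 0.5: 0.15 SD
- d = 0: no bias
- Negative d gives the same sizes against R2C-M.

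**Rejection under no effect**

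SE = √(1/n + 1/(n(1-p))).
- n = 70, p = 0.1, d = 0.25: SE = √(1/70 + 1/63) = 0.174, and rejection is 5.2%.
- n = 80, p = 0.3, d = 0.5: SE = √(1/80 + 1/56) = 0.174, bias/SE = 0.86, and rejection is 13.8%.

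A separate calculation in DUDIT points (102 per arm, SD 10, 70% attending, all assumed) gave a bias of 0.3 × 4 = 1.2 points and 12.3% rejection at a gap of 4 points, and 6.8% at a gap of 2.

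**Instrumental-variable estimate**

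Let e be the effect in R2C-M participants below two sessions. Then ITT = (1-p)(effect in attenders) + p·e, and

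IV = ITT/(1-p) = effect in attenders + e·p/(1-p).

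The gap d drops out. The price is the term in e:

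| e | p = 0.1 | p = 0.2 | p = 0.3 |
|---|---|---|---|
| 0 | 0 | 0 | 0 |
| 0.1 | 0.011 | 0.025 | 0.043 |
| 0.2 | 0.022 | 0.050 | 0.086 |
| 0.4 | 0.044 | 0.100 | 0.171 |

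The IV bias is below the restriction bias only while e·p/(1-p) < p·d, that is e < d(1-p). At d = 0.25 the limit is 0.175 to 0.225 SD; at d = 0.5 it is 0.35 to 0.45 SD.

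**Where each method fails**

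- Effect confined to attenders: a simulation with a true effect of -3 DUDIT points, 70% attending and gaps of 4 points either way gave restricted contrasts of -4.19 and -1.80, and IV estimates of -3.00 and -3.02.
- Same effect, 0.40 SD, in everyone, p = 0.2: the restricted contrast is 0.50, 0.40 or 0.30 for d = +0.5, 0 or -0.5. IV is 0.40/0.8 = 0.50 whatever the gap. Here IV is no better at a gap of 0.5 in size and worse at any smaller gap.

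**Precision**

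The IV standard error is √(2/n)/(1-p). At n = 80 and p = 0.2 the 95% half-widths are 1.96 × 0.158/0.8 = 0.39 SD for IV and 1.96 × 0.168 = 0.33 SD for the restriction.

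**The case against.** The strongest reply is that this is a labelled sensitivity analysis, limited to the DUDIT Total Score, with no decision resting on it, and that the SAP never claims it is an unbiased effect of attendance. That stands, and it limits the point to how a secondary result is built and read.

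A second reply is that the instrumental variable replaces one untestable assumption with another. That also stands. Participants below two sessions are still allocated workbooks and may have had session one. If they benefit as much as everyone else, IV overstates the effect by the factor 1/(1-p). The SAP's own dose rationale makes a full effect below two sessions less plausible, but does not exclude it. IV therefore belongs beside the existing analysis, not in its place.

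A reader might go further in three ways that the document does not support.
- That the restriction favours R2C-M. The sign follows the gap, which is unknown.
- That the SAP contradicts itself by using restriction for the DUDIT and IV for cost-effectiveness. Different methods for different outcomes are not a contradiction. The shared label and threshold do mean that the two results answer different questions, which the report should say.
- That controls are wholly unselected. They too need one follow-up assessment; they are unselected only on call attendance. The follow-up condition is itself post-randomisation and does not restore comparability.

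**Conclusion.** The concern holds for the per-protocol DUDIT analysis only. As specified, its contrast is biased by p·d: between 0 and 0.15 SD in either direction for 10 to 30% excluded and gaps up to 0.5 SD, with two-sided rejection under no effect of 5% to about 14%. All of these inputs are assumed, because the SAP gives no attendance rate or gap. If attendance is unrelated to untreated change, or nearly everyone attends, the bias is negligible. The intention-to-treat primary comparison is not affected. The change is worth making because it is cheap and uses a method already in the plan, not because the trial's main conclusion is at risk.

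**What to change.** Add a supplementary sensitivity analysis for 3-month DUDIT change: the instrumental-variable (complier) estimate, with randomised group as instrument for at least two sessions.

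- Compute it as the intention-to-treat contrast on the definitive scale, divided by the attendance share among all participants randomised to R2C-M.
- State the exclusion assumption (no effect below two sessions), and say that workbooks and session one could breach it.
- Show the shift e·p/(1-p) for e from 0 up to the full intention-to-treat effect.
- Describe the result as the intention-to-treat effect rescaled to attenders, not as independent confirmation.

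If the two-session comparison is kept, label it a non-randomised comparison and report the number excluded with their baseline DUDIT.

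The cost is a few sentences in the SAP, one further estimate and a wider interval: about 0.39 against 0.33 SD half-width at 20% excluded and 80 per arm, and 0.44 against 0.34 at 30%. No new data are needed.

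### The primary DUDIT contrast has no counsellor term: if counsellor effects differ between arms, its standard error is too small for conclusions beyond these counsellors

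*SAP*

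**What the plan says.** Under Study rationale and design, the experimental arm receives "four to six telephone-delivered intervention sessions, R2C-M workbooks and MA information booklet", and the control arm receives "four to six ≤5-min telephone check-ins" plus a booklet. The Analytic approach section treats the R2C-M contacts as counselling: the per-protocol rule requires, "for subjects randomised to the R2C-M arm, participation in at least two telephone counselling sessions". The SAP does not say who makes the control calls.

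Section 1 fixes the primary analysis: "Inferences about the effect of R2C on the primary outcome will be based on the comparison, between treatment groups", on their change from baseline to 3 months, and "this t-test will utilise the predicted means and their variance-covariance matrix that are recovered from the fitted mixed model". Steps 1 to 3 allow that model three error structures (independence or equicorrelation, AR(1), unstructured), chosen by AIC. All three describe correlation within a participant. Steps 1 to 6, which include the per-protocol analysis, contain no counsellor effect, fixed or random, and no cluster-robust variance.

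The counsellor appears in one place. The Analytic approach section lists "differences due to assigned counsellor" among covariates to be fitted, with their treatment interactions, in exploratory models that look for moderators and keep the most restricted model. Step 7 repeats most of that list for the DUDIT but leaves the counsellor out. The covariate table, which Step 7 describes as complete although its own heading presents it as examples, has no counsellor row.

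**The concern.** Participants treated by the same counsellor share whatever that counsellor adds or takes away. If this happens in the R2C-M arm only, or to a different extent in the two arms, the R2C-M mean carries a between-counsellor variance that the planned model does not estimate. The reported standard error then describes uncertainty about participants but not about counsellors, and a test meant to speak about the intervention in general rejects too often.

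The exploratory placement does not repair this. Those models come after the definitive analysis, they serve a different question, and the counsellor term may be dropped for parsimony. Because it is missing from Step 7 and the table, it may never be fitted to the DUDIT. If counsellors serve R2C-M alone, the planned counsellor-by-group interaction cannot be estimated at all.

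**Working it through.** **The plan's own figure.** "We planned to recruit between 188 and 204 individuals with mild to moderate MA use disorder". The increase is "an additional 8 subjects based on the 3 month attrition rate; or an additional 16 subjects based on the 6 month attrition rate": 188 + 8 = 196 and 188 + 16 = 204, which agrees with the stated maximum. The 188 itself cannot be re-derived, because the SAP gives no effect size, SD, alpha or power.

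**Inputs.**
- From the SAP: total N of 188 to 204.
- Assumed: 1:1 allocation (94 to 102 per arm), equal caseloads, two-sided 5% test, equal total variances, 4 to 10 counsellors (k), and ICC 0.01 to 0.05. The ICC is for change in DUDIT, since the contrast is of change.
- Attrition: none at first, then an assumed 25%. The SAP says attrition exceeded expectation but gives no rate.

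**Case A: counsellor effects in R2C-M only.** With m = (R2C-M participants)/k:
- design effect in that arm: DEFF = 1 + (m − 1) × ICC
- true SE / reported SE = √[(DEFF + 1)/2]
- true size = 2 × [1 − Φ(1.96 / SE ratio)]

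| N | k | m | ICC | DEFF | SE ratio | True size |
|---|---|---|---|---|---|---|
| 188 | 10 | 9.4 | 0.01 | 1 + 8.4 × 0.01 = 1.08 | √(2.084/2) = 1.02 | 5.5% |
| 204 | 6 | 17 | 0.03 | 1 + 16 × 0.03 = 1.48 | √(2.48/2) = 1.11 | 7.8% |
| 204 | 4 | 25.5 | 0.05 | 1 + 24.5 × 0.05 = 2.23 | √(3.225/2) = 1.27 | 12.3% |

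With 25% attrition in the last row, m = 25.5 × 0.75 = 19.1, DEFF = 1 + 18.1 × 0.05 = 1.91, the SE ratio is √(2.906/2) = 1.21 and the size is about 10.4%.

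**Check by simulation** (two-sample t-test that ignores counsellor, 94 per arm, 20,000 replicates): 5 counsellors with ICC 0.05 gave 10.7% against 10.3% from the formula. ICC 0 gave 5.0%.

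**Case B: the same counsellors serve both arms and shift them equally.** The counsellor effect cancels from the difference, so with balanced caseloads the true variance is (1 − ICC) times the reported one. At ICC 0.05 the SE ratio is √0.95 = 0.975 and the size about 4.4%. Simulation over ICC 0.02 to 0.10 gave 4.0% to 5.0%. The planned test is then slightly conservative.

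**The case against.** A reader might infer that the primary standard error is wrong as soon as counsellors differ. The document does not support that, for three reasons.

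First, the SAP never says that counsellors work in the R2C-M arm alone. A planned counsellor-by-group interaction makes sense only if staff serve both arms, and an equal shift in both arms causes no inflation. This stands as a condition. It does not remove the point, because calls of five minutes or less are unlikely to carry the same counsellor effect as counselling sessions, and effects that differ by arm still inflate the error.

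Second, participants are randomised individually. If R2C-M does nothing with any counsellor, there is no counsellor-specific treatment effect and the nominal size holds. If the counsellors are regarded as fixed and participants fall to them at random, the planned standard error is about right for those counsellors. Inflation concerns a mean effect of zero over a wider population of counsellors. This also stands. The SAP's stated aim is the efficacy of the intervention, which most readers will take to reach beyond the staff employed, but it does not define that target.

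Third, everything in the calculation except N is assumed. The low end is trivial, and the top end combines the fewest counsellors with the highest ICC and full retention. Counsellor numbers and assignment may be in the published protocol, so their absence here is not a fault. The point rests only on what the SAP does fix: the primary model and the place it gives to the counsellor.

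**Conclusion.** The point holds conditionally. The primary contrast has no protection against clustering by counsellor, and the exploratory moderator models provide none. Its standard error is too small if counsellor effects are confined to R2C-M or differ between arms and the result is meant to generalise beyond these counsellors. If shared staff shift both arms equally, it is not too small.

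Under the stated assumptions for the R2C-M-only case, the understatement ranges from negligible (2%, size 5.5%) to large enough to decide a borderline result (27%, size 12.3%, or about 10.4% with 25% attrition). The SAP cannot place the trial within that range. This justifies a cheap addition, not a claim that the primary analysis is invalid.

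**What to change.** Before the statistician is unblinded, add one named sensitivity analysis of the 3-month DUDIT contrast with a counsellor random effect on post-baseline change:
- if counsellors serve R2C-M only, fit the effect in that arm alone (a partially nested model);
- if staff are shared, fit counsellor and counsellor-by-arm random effects.

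Use small-sample degrees of freedom (Kenward-Roger or Satterthwaite). State who makes the control calls. Report the number of counsellors, their caseloads and the estimated ICC beside the primary result.

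Bring the Analytic approach list, Step 7 and the covariate table into agreement on the counsellor. Drop the counsellor-by-group moderator term only if counsellors serve R2C-M alone, because it then cannot be estimated. If staff are shared, it can be estimated and is worth keeping.

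The cost is one extra model on data the plan already intends to use. With few counsellors the variance component is poorly estimated and the interval will be wider and less stable, which is why the primary model should stay unchanged.

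### The primary DUDIT contrast is valid, but the model as described makes no adjustment for baseline DUDIT, so the primary confidence interval may be wider than the data require

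*SAP*

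**What the plan says.** In the SAP's section 1 on the DUDIT, the primary inference is the "comparison, between treatment groups, of their changes from baseline to 3 months follow-up". It uses predicted means and their covariance matrix from a fitted "mixed model for all repeated assessments up to and including 12 months". The section headed Analytic approach describes the same test, which "will be based on a t-test of the corresponding interaction contrast". Baseline DUDIT is therefore one of the response occasions.

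Neither place says that the arms share a baseline mean or that baseline DUDIT is a covariate. The adjustments that are listed are exploratory. Analytic approach names "baseline levels of MA use, psychological distress, depression, anxiety and stress", and step 7 names, where appropriate, "level of methamphetamine use at baseline (and interactions with treatment group"). Neither names baseline DUDIT, and the covariate table at the end of the SAP does not list it. Baseline adjustment is specified only for the regressions under Cost-effectiveness analysis.

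For the covariance, step 3 will "investigate three alternative error variance/covariance models (VCVMs"): equicorrelation, AR(1) and unstructured. It takes the smallest AIC "unless a more parsimonious model has an AIC within 10 units of the minimum AIC".

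**The concern.** In a group-by-time model with a free baseline mean in each arm, the change contrast subtracts the observed baseline difference with coefficient 1. Under randomisation that difference is chance. The efficient coefficient is the slope of the 3-month score on baseline, which is usually below 1. The excess subtraction adds noise to the primary estimate.

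This causes no bias and no inflation of type I error. What is at stake is the width of the primary interval, in a trial whose target was raised from 188 to as many as 204 because attrition exceeded expectation (Study rationale and design). Baseline DUDIT is already collected, so any precision recovered needs no further recruitment.

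**Working it through.** **The plan's own figures.** The SAP gives no DUDIT SD, correlation, effect size or attrition rate, so neither 188 nor the planned precision can be re-derived. Only the increments can be checked: 188 + 8 = 196 and 188 + 16 = 204, which agree with the text.

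**Inputs.** From the SAP: four DUDIT occasions (baseline, 3, 6 and 12 months), a mixed model, and the 3-month change contrast. Assumed: n per arm (1:1 allocation), s0 and s1 the baseline and 3-month SDs, k = s0/s1, ρ the correlation of baseline with 3 months, and monotone dropout.

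**Complete data.**

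- Change contrast: Var = (2/n)(s0² + s1² − 2ρ·s0·s1)
- Baseline-adjusted contrast: Var = (2/n)·s1²(1 − ρ²)
- Excess: (2/n)(s0 − ρ·s1)², never negative, and zero only when k = ρ
- Variance ratio, adjusted to change: (1 − ρ²) / [(1 − ρ²) + (k − ρ)²]

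Example, k = 1 and ρ = 0.5: 0.75 / (0.75 + 0.25) = 0.75. The interval shrinks by 1 − √0.75 = 13%.

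| k | ρ = 0.3 | ρ = 0.5 | ρ = 0.7 |
|---|---|---|---|
| 0.67 | 0.87 | 0.96 | 0.998 |
| 0.75 | 0.82 | 0.92 | 0.995 |
| 1 | 0.65 | 0.75 | 0.85 |
| 1.33 (extreme) | 0.46 | 0.52 | 0.56 |

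At k = 1 the interval is 19%, 13% and 8% narrower. At k = 1.33 it is 32%, 28% and 25% narrower.

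**With dropout.** Baseline, as a response, then carries some information about missing follow-up, and the gain shrinks. If a proportion p has a 3-month score, replace (1 − ρ²) by (1 − ρ²)/p in both places. Example, k = 1, ρ = 0.5, p = 0.85: 0.882 / (0.882 + 0.25) = 0.78. A four-occasion generalised least squares calculation gives the same values:

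| Dropout at 3/6/12 months | k | ρ = 0.3 | ρ = 0.5 | ρ = 0.7 |
|---|---|---|---|---|
| 15/20/25% | 0.75 | 0.84 | 0.93 | 0.996 |
| 15/20/25% | 1 | 0.69 | 0.78 | 0.87 |
| 25/35/40% | 0.75 | 0.86 | 0.94 | 0.996 |
| 25/35/40% | 1 | 0.71 | 0.80 | 0.88 |

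An AR(1) truth with the same baseline to 3-month correlation gives the same ratios. A simulation fitting the mixed model by REML (150 runs, 94 per arm, ρ = 0.5, k = 1, dropout 20/30/35%) gave mean standard errors of 0.159 with free and 0.141 with common baseline means, a ratio of 1.126 against 1.125 in theory.

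**In participants.** At k = 1, ρ = 0.5 and complete data, the adjusted analysis of 0.75 × 204 = 153 participants would be as precise as the planned analysis of 204. With 20/30/35% dropout it would need 204/1.125² ≈ 161.

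**Worst case for adjustment.** At k = ρ nothing is gained, and covariate adjustment costs a factor 1 + 1/(2n − 4) in variance: 1 + 1/156 = 1.006 at 80 per arm, and 1 + 1/184 = 1.005 at 94.

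**Interaction with step 3.** A common baseline mean fitted under common-variance equicorrelation can lose precision when the true SDs differ. At ρ = 0.7 and complete data, its variance relative to the free-baseline contrast is 1.12, 1.06, 1.02 and 0.98 at k = 0.67, 0.75, 0.80 and 0.85. Equicorrelation has 2 parameters and unstructured has 10, so under the 10-unit rule unstructured must improve −2logL by more than 2 × 8 + 10 = 26. With 188 participants, ρ = 0.7 and complete data, equicorrelation would be kept in under 0.1%, 2.5% and 70% of trials at k = 0.67, 0.75 and 0.85. The larger losses are therefore rarely reached, and fixing the covariance removes them.

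**The case against.** The strongest reply is that nothing is wrong. The primary outcome is defined as change, the contrast tests that change, and the model is conventional and coherent. A more efficient estimator does not make the planned one an error. This stands, and it is why the point is only a suggestion about precision.

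Second, the SAP does not write out the fixed effects, and it supplements a published protocol that is not at hand. A common baseline mean may be intended. That cannot be excluded, but nothing in the SAP says so, and an interaction contrast of changes ordinarily implies free baseline means. If a common mean is intended, one sentence settles the matter.

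Third, the gain may be small. Recruitment is limited to mild to moderate disorder, which may narrow baseline DUDIT. Data are to be analysed as stratified, but the SAP does not name the factor; one related to severity would leave less imbalance to correct. At k = 0.67 to 0.75 and ρ = 0.5 to 0.7 the interval narrows by only 0.1% to 4%. Nothing in the SAP favours k = 1.33, although a floor effect at follow-up could push k above 1. This limits the size, not the direction.

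Fourth, changing the primary estimator this late has a credibility cost, and a sensitivity analysis would capture part of the benefit. The cost is real. It is acceptable only if the change is dated, reasoned and made blind to allocation.

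**Conclusion.** The point holds as a matter of efficiency. As described, the primary contrast is valid and unbiased, but in large samples its variance is never below that of the baseline-adjusted contrast and exceeds it unless k = ρ. For equal SDs and ρ from 0.3 to 0.7, the avoidable width is 19% to 8% of the interval with complete data, about 17% to 7% with 15% missing at 3 months, and about 16% to 6% with 25% missing. It approaches nil as k nears ρ.

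These figures rest on assumed SD ratios, correlations and dropout, and on reading the model as having free baseline means. If step 2 selects the transformed scale, k and ρ refer to that scale. The change is worth considering, because the possible gain is appreciable and the worst-case penalty is about half a percent in variance.

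**What to change.** Before the statistician is unblinded, and as a dated and reasoned change, keep the 3-month group difference as the primary contrast and write out the fixed effects with one of these adjustments:

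- **(a) Preferred.** Keep baseline DUDIT as a response, give both arms a common baseline mean, and fix an unstructured covariance (or one that lets the baseline variance differ), exempt from the 10-unit AIC rule. This keeps all randomised participants, in line with an analysis that "will be based on the intention-to-treat principle". It fixes 10 covariance parameters in place of the step 3 selection.
- **(b) Alternative.** Model the 3, 6 and 12 month scores with baseline DUDIT by visit as a covariate. This costs about one degree of freedom per visit. Participants with no follow-up DUDIT leave the model, so the analysis set must be redescribed; the SAP currently makes having a follow-up assessment a condition of the per-protocol set only.

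The two options agree to three decimals in every case computed. The common-baseline constraint should not be paired with common-variance equicorrelation.

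If unblinding has already occurred, keep the planned contrast as primary and report the adjusted model as a labelled sensitivity analysis. No new data are needed. The main cost is a late change to the primary estimator of a plan finalised on 1 August 2025.
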